6.4 Effectiveness Analyses

This study defines one primary endpoint [REDACTED] The Safety Analysis Set will serve as the primary set for all effectiveness analyses.

6.4.1 Primary Effectiveness

The primary objective of this study is to evaluate the overall performance of DD T2 lenses when compared to Clariti 1 Day lenses. The primary endpoint is the subjective rating of overall quality of vision, collected binocularly on a scale of 1 (Poor) to 10 (Excellent) at the Day 8 Follow-up visits.

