3 INTRODUCTION

3.1 Study Rationale and Purpose

The purpose of this study is to obtain on-eye performance data to inform contact lens product development and to further evaluate product performance in the intended population. The primary endpoint was selected to fulfill the primary objective of the study. Procedures for measurement of these endpoints were selected based on common practice for these assessments. The design of this study is justified based upon preclinical and clinical testing, as described within the Investigator's Brochure. Clariti 1 Day contact lenses were chosen as the control product because these lenses have the same wear modality. The new contact lens in development is intended for the optical correction of refractive myopia in persons with non-diseased eyes.

There are no immediate plans to submit the results of this study for publication; however, the results may be offered for publication if they are of scientific interest, or if the results relate to a product that is subsequently approved or cleared for marketing.

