3.2 Trial Objective

The primary objective of this study is to evaluate the overall performance of DD T2 lenses when compared to Clariti 1 Day lenses.

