6.4.1.1 Statistical Hypotheses

[figure not shown]
No inferences are to be made on the primary effectiveness endpoint; therefore, no hypotheses are formulated.

[figure not shown]
[figure not shown]

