6.4.2 Secondary Effectiveness

No secondary objective or endpoint is defined for this study.

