1.1 Study Objectives

PRIMARY OBJECTIVE

The primary objective of this study is to evaluate the overall performance of DD T2 lenses when compared to Clariti 1 Day lenses.

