4.1 Effectiveness Endpoints

[figure not shown]
Primary Endpoint

The primary endpoint is the subjective rating on overall quality of vision, collected binocularly on a scale of 1 (Poor) to 10 (Excellent) at the Day 8 Follow-up visits.

Secondary Endpoint

No secondary endpoint is defined for this study.

[figure not shown]

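### Does a single vision rating leave the broad primary objective of overall lens performance undefined?

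*Protocol*

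**What the plan says.** Protocol 3.2 sets the aim: "The primary objective of this study is to evaluate the overall performance of DD T2 lenses" against the control lens. SAP 1.1 repeats it: "evaluate the overall performance of DD T2 lenses when compared to Clariti 1 Day lenses". The same objective appears in the Protocol synopsis, in Protocol 6.4.1 and in the SAP Executive Summary. None of these places breaks it into components.

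The endpoint is specific. Protocol 6.4.1 says "The primary endpoint is the subjective rating of overall quality of vision", and SAP 4.1 agrees: "The primary endpoint is the subjective rating on overall quality of vision". It is rated binocularly from 1 to 10 at the Day 8 follow-up visits. Protocol 3.1 supplies the only visible sentence joining the two: "The primary endpoint was selected to fulfill the primary objective of the study".

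Protocol 6.4.2 adds that "No secondary objective or endpoint is defined for this study". Protocol 6.4 opens with "This study defines one primary endpoint", after which text is blacked out. On inference, Protocol 6.4.1.1 states: "No inferences are to be made on the primary effectiveness endpoint; therefore, no hypotheses are formulated". The SAP Executive Summary says that success criteria do not apply.

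**The concern.** Overall performance of a contact lens could cover more than how well the wearer thinks they see. If the stated aim is broad and the only visible primary measure is a vision rating, a reader may ask which results answer the aim.

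The visible text does not say whether Snellen acuity with the study lenses, adverse events, biomicroscopy or device deficiencies count towards it. With no secondary endpoint and no decision rule, the wording of objective and endpoint has to settle what the study can claim. If the vision rating favoured one lens and another measure favoured the other, the report's authors would have to choose how to describe the objective. A result on vision alone might then be presented as a finding about the lens as a whole.

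**Working it through.** No figure in the documents depends on this point, so the check sets the passages side by side.

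1. **Is the objective defined anywhere visible?** No. All five statements of it (Protocol synopsis, 3.2 and 6.4.1; SAP Executive Summary and 1.1) carry the same aim without components. Table 7-1 of the Protocol explains intended performance under its entry for malfunction, but that is a different concept.

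2. **Is the choice of endpoint justified?** Only by the sentence in Protocol 3.1. The sentence after it defends the measurement procedures by common practice, not the choice of endpoint. The same section does say that the lens is meant to correct myopia optically. For such a device the wearer's own rating of vision bears directly on its purpose, although the Protocol does not draw that connection.

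3. **Could the rest be in hidden text?** Quite possibly.
   - The synopsis has a gap between the primary effectiveness endpoint and the safety endpoints.
   - The Protocol contents list has three blacked-out entries between 6.4.2 and 6.5, as many as the entries for 6.4.1 and its two subsections.
   - The SAP contents list has a blacked-out entry directly after 4.3.1.
   - Table 1-1 shows one of seven subjective rating items; the other six are blacked out.
   - Protocol 3.1 and 6.7 and SAP 4.4 speak of endpoints in the plural.

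   This suggests, without proving it, that other effectiveness endpoints were pre-specified.

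4. **What would differ under a narrow and a broad reading of the objective?**

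| Element | Vision rating only | Vision rating plus other measures |
|---|---|---|
| Data collected (Table 1-1) | same | same |
| Primary summary (SAP 4.3.1): descriptive statistics, 95% interval for each lens mean, five rating categories | same | same |
| Safety tables and listings (SAP 5.3.1 to 5.3.3) | same | same |
| Hypotheses, multiplicity, success criteria | none | none |
| Target of 20 completers, about 22 enrolled | same | same |

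No row changes. The visible text derives neither 20 nor 22 from an effect size, so the reading of the objective cannot alter the sample size.

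5. **What would a clarifying sentence add?** It could list the measures that describe performance, give the reason for making vision primary, and say that each measure is summarised separately. The last is already how the visible plan works: no composite is defined, and the rating and the safety endpoints each have their own summaries. The list and the reason would be new text, but they would produce no new analysis.

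**The case for a change.** The strongest case for a change is that it is cheap and that descriptive status does not remove the question. Protocol 3.1 says the study is to inform product development, so readers will act on the comparison even without a test. That section and 6.4.1 are where a rationale would naturally stand; their visible text gives none, and a list of further endpoints, even if one is hidden, would not explain why vision was made primary. Protocol 3.3 names ocular discomfort as a potential harm, and a vision rating need not capture it. Snellen acuity is listed in the synopsis as an effectiveness assessment but has no visible endpoint status.

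Part of this stands. The missing reason is real, and a rating of vision quality would not by itself support a statement about overall performance. The rest is weaker. The discomfort example describes the public copy more than the trial, because six of the seven rating items cannot be read. The worry that authors will choose their answer after seeing results has little room: the primary measure, its scale, its timing and its summaries are pre-specified, as are the safety tables. The authors could choose a phrase, but not a different primary result.

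**Conclusion.** The observation is accurate but calls for no change. The objective is broader than the one visible primary endpoint, and Protocol 3.1 asserts the link without arguing it. A broad aim with one specific primary measure is a drafting choice in a descriptive study of about 22 subjects, and the passages do not contradict each other. An analyst following the plan as written would produce the same data, tables and descriptive results as one working from an expanded text. The effect on estimates, error rates and decisions is nil.

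This rests on two things: the study stays descriptive, as Protocol 6.4.1.1 and the SAP Executive Summary state, and the report calls the primary result what the endpoint definition calls it, a rating of overall quality of vision. A sentence of rationale would be harmless but optional, and the unredacted text may already contain it. The judgement would differ if the study carried a success criterion or supported a formal claim of overall performance; neither appears in the visible documents.

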6.4.1.1 Statistical Hypotheses

[figure not shown]
No inferences are to be made on the primary effectiveness endpoint; therefore, no hypotheses are formulated.

[figure not shown]
[figure not shown]
6.4.1.2 Analysis Methods

Descriptive statistics will be provided.

6.4.2 Secondary Effectiveness

No secondary objective or endpoint is defined for this study.

6.5 Subgroup Analyses

It is not expected that demographic or baseline characteristics will have an impact on the study results in this study. No subgroup analyses are planned.

6.6 Handling of Missing Data

All data obtained in evaluable subjects/eyes will be included in the analysis. No imputation for missing values will be carried out for the primary analysis.

6.7 Multiplicity

No multiplicity adjustment needs to be considered for the effectiveness endpoints since no formal hypothesis testing will be conducted.

6.8 Safety Analysis

The safety endpoints for this study are AEs, biomicroscopy findings, and device deficiencies.

Descriptive summaries (counts and percentages) for ocular and nonocular AEs will be presented by Medical Dictionary for Regulatory Activities Preferred Terms. AEs leading to study discontinuation, significant non-serious AEs, and SAEs will be identified. Individual subject listings will be provided, as necessary.

Individual subject listings will be provided for AEs that occur after signing informed consent but prior to exposure to study lenses.

[figure not shown]
Each biomicroscopy parameter will be tabulated by its grade. For each biomicroscopy parameter, counts and percentages of eyes that experience an increase of ≥ 2 grades from Baseline (Visit 1) to any subsequent visit will be presented. A supportive listing will be generated which will include all biomicroscopy data from all visits for these eyes experiencing the increase.

Two listings (prior to exposure of study lenses and treatment-emergent) of device deficiencies, as recorded on the Device Deficiency Form, will be provided. Additionally, each device deficiency category will be tabulated.

No inferential testing will be conducted for the safety analyses.

6.9 Interim Analyses

There are no plans to conduct an interim analysis and no criteria by which the study would be terminated early based upon statistical determination.

7 ADVERSE EVENTS AND DEVICE DEFICIENCIES

Table 7-1 Terms and Definitions

Adverse event (AE)	
Any untoward medical occurrence, unintended disease or injury, or untoward clinical signs (including abnormal laboratory findings) in subjects, users or other persons, whether or not related to the investigational medical device (test product).
 
Note: For subjects, this definition includes events related to the test product, the control product, or the procedures involved. For users or other persons, this definition is restricted to events related to the test product.

--------------------	--

Adverse device effect (ADE)	
AE related to the use of an investigational medical device (test product) or control product.
 
Note: This definition includes AEs resulting from insufficient or inadequate instructions for use, deployment, implantation, installation, or operation; any malfunction; and use error or intentional misuse of the test product or control product.

Anticipated serious adverse device effect (ASADE)	
Serious ADE which by its nature, incidence, severity or outcome has been identified in the risk management file.

Device deficiency	
Inadequacy of a medical device with respect to its identity, quality, durability, reliability, safety, or performance.
 
Note: This definition includes malfunctions, use errors, and inadequate labeling.

Malfunction	
Failure of a medical device to meet its performance specifications or otherwise perform as intended. Performance specifications include all claims made in the labeling of the device. The intended performance of the device refers to the intended use for which the device is labeled or marketed.

Non-serious adverse event	
AE that does not meet the criteria for an SAE.

Serious adverse event (SAE)	
AE that led to any of the following:
 
 • Death. • A serious deterioration in the health of the subject that either resulted in: 
 a) a life-threatening illness or injury. 
Note: Life-threatening means that the individual was at immediate risk of death from the event as it occurred, ie, it does not include an event which hypothetically might have caused death had it occurred in a more severe form.
 
 b) any potentially sight-threatening event or permanent impairment to a body structure or a body function. c) in-patient hospitalization or prolonged hospitalization. 
Note: Planned hospitalization for a pre-existing condition, without serious deterioration in health, is not considered an SAE. In general, hospitalization signifies that the individual remained at the hospital or emergency ward for observation and/or treatment (usually involving an

	
overnight stay) that would not have been appropriate in the physician's office or an out-patient setting. Complications that occur during hospitalization are adverse events. If a complication prolongs hospitalization or fulfills any other serious criteria, the event is serious. When in doubt as to whether "hospitalization" occurred, the event should be considered serious.
 
d) a medical or surgical intervention to prevent a) or b). e) any indirect harm as a consequence of incorrect diagnostic test results when used within manufacturer's instructions for use.
 
 • Fetal distress, fetal death, or a congenital abnormality or birth defect. 
Refer to Section 7.1 for additional SAEs.

Serious adverse device effect (SADE)	ADE that has resulted in any of the consequences characteristic of an SAE.
Significant non-serious adverse event	A significant non-serious AE is a symptomatic, device-related, non-sight threatening AE that warrants discontinuation of any contact lens wear for greater than or equal to 2 weeks. Refer to Section 7.1 for additional Significant Non-Serious AEs.
Unanticipated serious adverse device effect (USADE)	Serious adverse device effect which by its nature, incidence, severity or outcome has not been identified in the risk management file.
Use Error	Act or omission of an act that results in a different medical device response than intended by manufacturer or expected by user. Note: This definition includes slips, lapses, and mistakes. An unexpected physiological response of the subject does not in itself constitute a use error.

7.1 General Information

An AE is any untoward medical occurrence, unintended disease or injury, or untoward clinical signs (including abnormal laboratory findings) in subjects, users, or other persons, whether or not related to the investigational medical device (test *article*).

Figure 7-1 **Categorization of All AEs**

[figure not shown]
[figure not shown]

Figure 7-2 **Categorization of All Serious Adverse Events**

Serious Adverse Events

In addition to reporting all AEs (serious and non-serious) meeting the definitions, the Investigator must report any occurrence of the following as an SAE:

- An ocular infection including a presumed infectious ulcer with any of the following characteristics:

- Central or paracentral location
 - Penetration of Bowman's membrane
 - Infiltrates > 2 mm diameter
 - Iritis
 - Increase in intraocular pressure
 - Culture positive for microorganisms
 - Increasing size or severity at subsequent visits
- Any central or paracentral corneal event (such as neovascularization) that results in permanent opacification
 - Hypopyon
 - Hyphema
 - Neovascularization within the central 6 mm of the cornea
 - Permanent vision loss as defined by loss of 2 or more lines of BCVA from enrollment visit that fails to resolve
 - Uveitis (anterior, intermediate, or posterior)
 - Corneal abrasion affecting $\geq 50\%$ of corneal surface area

Significant Non-Serious Adverse Events

A significant non-serious AE is a symptomatic, device-related, non-sight threatening AE that warrants discontinuation of any contact lens wear for greater than or equal to 2 weeks. In addition, the Investigator must report any occurrence of the following as a Significant Non-Serious AE:

- Peripheral non-progressive non-infectious ulcers
- All symptomatic corneal infiltrative events
- Corneal staining score greater than or equal to Grade 3 (Refer to MOP for grading scales) [Grading scale is based on ISO 11980:2012 unless specified differently in MOP]
- Temporary vision loss as defined by loss of 2 or more lines of BCVA from enrollment visit that persists for 2 or more weeks
- Neovascularization score greater than or equal to Grade 2

The above events are based upon the categories provided in the ISO 11980:2012 and the US FDA Premarket Notification (510(k)) Guidance Document for Daily Wear Contact Lenses and Contact Lens Care Products.

Device Deficiencies

A device deficiency is inadequacy of a medical device with respect to its identity, quality, durability, reliability, safety, or performance. A device deficiency may or may not be associated with patient harm (ie, ADE or SADE); however, not all ADEs or SADEs are due to a device deficiency. The Investigator should determine the applicable category listed in the Device Deficiency eCRF for the identified or suspect device deficiency and report any patient harm separately. Examples of device deficiencies include the following:

- Failure to meet product specifications (eg, incorrect lens power/diameter/base curve/color)
- Lens cloudy
- Lens surface/edge defect
- Torn lens during handling/in pack
- Packaging deficit (eg, mislabeled product, tampered seal, leaking bottle/container)
- Suspect product contamination
- Lack of performance

7.2 Monitoring for Adverse Events

At each visit, after the subject has had the opportunity to spontaneously mention any problems, the Investigator should inquire about AEs by asking the standard questions:

- “Have you had any health problems since your last study visit?”
- “Have there been any changes in the medicines you take since your last study visit?”

Additionally, changes in *any protocol-specific parameters and/or questionnaires* evaluated during the study are to be reviewed by the Investigator. Any untoward (unfavorable and unintended) change in *a protocol-specific parameter or questionnaire response* that is clinically relevant, in the opinion of the Investigator, is to be reported as an AE. These clinically relevant changes will be reported regardless of causality.

7.3 Procedures for Recording and Reporting

AEs are collected from the time of informed consent. Any pre-existing medical conditions or signs/symptoms present in a subject prior to the start of the study (ie, before informed consent is signed) are not considered AEs in the study and should be recorded in the Medical History section of the eCRF.

In addition, temporary lens awareness or visual changes during the fitting process are not considered AEs if the Investigator assesses that the symptom(s) can reasonably resolve within the anticipated adaptation period.

- ADEs or SAEs are documented on the *Serious Adverse Event and Adverse Device Effect* eCRF within 24 hours of the Investigator's or site's awareness.
- Device deficiencies are documented on the *Device Deficiency* eCRF within 24 hours of the Investigator's or site's awareness.
- A printed copy of the completed *Serious Adverse Event and Adverse Device Effect* and/or *Device Deficiency* eCRF must be included with product returns.
- Additional relevant information after initial reporting must be entered into the eCRF as soon as the data become available.
- Document any changes to concomitant medications on the appropriate eCRFs.
- Document all relevant information from Discharge Summary, Autopsy Report,
- Certificate of Death, etc, if applicable, in narrative section of the *Serious Adverse Event and Adverse Device Effect* eCRF.

Note: Should the EDC system become non-operational, the site must complete the appropriate paper *Serious Adverse Event and Adverse Device Effect* and/or *Device Deficiency* Form. The completed form is emailed to the Study Sponsor at [contact] according to the timelines outlined above; however, the reported information must be entered into the EDC system once it becomes operational.

Any AEs and device deficiencies for non-study marketed devices/products will be considered and processed as spontaneous (following the postmarket vigilance procedures) and should be communicated to the device's/product's manufacturer as per local requirements.

Study Sponsor representatives may be contacted for any protocol related question and their contact information is provided in the MOP that accompanies this protocol.

Further, depending upon the nature of the AE or device deficiency being reported, the Study Sponsor may request copies of applicable portions of the subject's medical records. The Investigator must also report all AEs and device deficiencies that could have led to a SADE according to the requirements of regulatory authorities or IRB/IEC.

Intensity and Causality Assessments

Where appropriate, the Investigator must assess the intensity (severity) of the AE based upon medical judgment with consideration of any subjective symptom(s), as defined below:

Intensity (Severity)

- | | |
|----------|--|
| Mild | An AE is mild if the subject is aware of but can easily tolerate the sign or symptom. |
| Moderate | An AE is moderate if the sign or symptom results in discomfort significant enough to cause interference with the subject's usual activities. |
| Severe | An AE is severe if the sign or symptom is incapacitating and results in the subject's inability to work or engage in their usual activities. |

For every AE in the study, the Investigator must assess the causality (Related or Not Related to the medical device or study procedure). An assessment of causality will also be performed by Study Sponsor utilizing the same definitions, as shown below:

Causality

- | | |
|-------------|--|
| Related | An AE classified as related may be either definitely related or possibly related where a direct cause and effect relationship with the medical device or study procedure has not been demonstrated, but there is a reasonable possibility that the AE was caused by the medical device or study procedure. |
| Not Related | An AE classified as not related may either be definitely unrelated or simply unlikely to be related (ie, there are other more likely causes for the AE). |

The Study Sponsor will assess the AEs and may upgrade the Investigator's assessment of seriousness and/or causality. The Study Sponsor will notify the Investigator of any AEs that are upgraded from non-serious to serious or from unrelated to related.

